3.1.3.1 Clinical Experience to Date: Data from the Phase 1/1b 516-001 study

The 516-001 trial was a Phase 1/1b dose escalation study that explored the safety, PK, and optimal MGCD516 dose ranges. The following is a summary of experience generated in this first-in-human study. Data collection is ongoing, thus all data reported are preliminary.

The modified toxicity probability interval (mTPI) method¹⁸ was used to guide dose escalation. The assumptions applied in establishing the mTPI methodology were:

- the Maximum Tolerated Dose (MTD) was defined to have a 0.3 probability of dose limiting toxicity; and
- the acceptable variance around the MTD was ± 0.05 (i.e., the region of the MTD was 25% to 35% incidence of dose limiting toxicity).

Dose escalation in cohorts of patients started at 10 mg MGCD516 daily and proceeded through 20, 40, 80, 110, 150 and 200 mg daily. Cohorts included 4 to 7 patients. A total of 32 patients were accrued, and in November 2015, the dose of 200 mg MGCD516 administered daily was determined to exceed the MTD.

The observed safety profile for MGCD516 was manageable and, in most respects, expected for small molecule tyrosine kinase inhibitors that inhibit VEGFR. Adverse events (AEs) reported to

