With regards to the clinical efficacy of MGCD516, as of 11/18/2016, 32 patients were enrolled in the Phase 1 dose escalation portion of the Phase 1/1b 516-001 study, of which 27 patients had at least one imaging study. Of these 27 patients, 17 showed stable disease (SD) and 10 showed progressive disease (PD) as best response. The phase 1b portion is treating patients with a starting dose of 150 mg as the MTD based on the dose escalation portion. It has enrolled 35 patients, of which 25 patients have had at least one imaging study. Of these 25 patients, 4 have shown partial response (PR), 17 have shown SD, and 4 have shown PD as best response. Out of the 4 patients that have demonstrated PR, one has metastatic ccRCC refractory to prior anti-VEGF therapy and has achieved a durable response, one has metastatic castration-resistant prostate cancer, one has refractory breast cancer with RET mutation, one has previously treated non-small cell lung cancer with RET rearrangement. A total of 8 patients with RCC have been treated to date. The majority have had some degree of tumor reduction but only the 1 case mentioned above has achieved PR by Response Evaluation Criteria in Solid Tumors (RECIST) criteria.

The updated Investigator's Brochure (IB) issued on 25 August 2015 includes preliminary PK and PD data collected in the 10 mg to 110 mg cohorts. After single dose administration, MGCD516 reaches peak concentration in a median time of 3 to 9 hours. Exposure parameters (maximum concentration [C_{max}] and area under the curve [AUC]) are dose proportional with doses up to 110 mg. Mean elimination half-life varies between 40 and 53 hours. The steady state PK is reached in a mean time of 11 to 15 days. Drug accumulation is observed after administration of multiple doses and averages 4.2-fold for C_{max} and 4.7-fold for AUC_{0-24} . Preliminary PK data generated since the IB update indicate that increase in exposure continues to be dose proportional through the 200 mg daily dose level, the highest dose administered.

As described in the IB update, the PD effects of MGCD516 treatment are examined by analyzing VEGFA, soluble VEGF-R2 and soluble MET ectodomain (sMET) levels in plasma samples collected before and after MGCD516 administration. Preliminary PD analyses showed a concentration dependent modulation of each biomarker that approached near maximal level (based on historical data for TKIs) for VEGF-A (~300% increase), sVEGF-R2 (~35% decrease),

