4.0 ELIGIBILITY CRITERIA

4.1 Signed written informed consent

1. Patients must give written informed consent prior to initiation of therapy, in keeping with the policies of the institution. Patients with a history of major psychiatric illness must be judged able to fully understand the investigational nature of the study and the risks associated with the therapy.

4.2 Inclusion criteria:

1. Patients with histologically or cytologically confirmed metastatic/advanced clear cell RCC, or RCC with a clear cell component, who have received 1 or 2 prior anti-angiogenic therapy regimens (+/- cytokine therapy with interleukin-2 or interferon-alfa) in the advanced or metastatic setting. Examples of anti-angiogenic agents include, but are not limited to, sorafenib, sunitinib, pazopanib, axitinib, and bevacizumab.
2. There must be evidence of progression on or after last treatment regimen received and within 6 months of enrollment.
3. Patients must have at least one measurable site of disease, defined as a lesion that can be accurately measured in at least one dimension (longest diameter to be recorded) and measures \geq 15 mm with conventional techniques or \geq 10 mm with more sensitive techniques such as MRI or spiral CT scan. If the patient has had previous radiation to the marker lesion(s), there must be evidence of progression since the radiation.
4. Karnofsky performance status \geq 70

5. Age \geq 18 years
6. Patients must have adequate organ and marrow function prior to study entry as defined below:
 - Hemoglobin^a \geq 9 g/dl (treatment allowed)
 - absolute neutrophil count \geq 1,500/ μ L
 - platelets \geq 100,000/ μ L
 - total bilirubin \leq 1.5 mg/dl
 - AST(SGOT) or ALT (SGPT) \leq 2.5 X institutional uln, except in known hepatic metastasis, wherein may be \leq 5 x ULN
 - Serum Creatinine \leq 1.5 x ULN (as long as patient does not require dialysis)

^a May receive transfusion

^bIf creatinine is not $<1.5 \times$ ULN, then calculate by Cockcroft-Gault methods or local institutional standard and CrCl must be \geq 40 mL/kg/1.73 m²

7. INR and PTT \leq 1.5 x ULN prior to study entry. Therapeutic anticoagulation with warfarin is allowed if target INR \leq 3 on a stable dose of warfarin or on a stable dose of low molecular weight (LMW) heparin for $>$ 2 weeks (14 days) at the time of enrollment.

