6.3 Concomitant Therapies

The following considerations apply during the entire duration of the study:

- No other approved or investigational anticancer treatment will be permitted during the study period, including chemotherapy, biologic agents, hormone therapy or immunotherapy except for bisphosphonates. No other investigational drug may be used during treatment on this protocol, and concurrent participation in another therapeutic clinical trial is not allowed.
- No anticancer agents other than the study medications should be given to patients. If such agents are required for a patient then the patient must first be withdrawn from the study.
- Surgery or radiation therapy for palliation purposes or management of intercurrent illness which, in the judgement of the treating physician, is not related to disease progression. After the patient has received at least 2 infusions of nivolumab and 6 weeks (42 days) of oral MGCD516 then further therapy on protocol can be held for up to 4 weeks (28 days) to allow for recovery from surgical or other interventions.
- Growth factors (e.g. G-CSF, GM-CSF, erythropoietin, platelets growth factors etc.) are not to be administered prophylactically but may be prescribed by the investigator for rescue from severe hematologic events, if this is thought to be appropriate.
- No chronic treatment with systemic steroids or other immunosuppressive agents. Topical or inhaled corticosteroids are allowed.
- Live vaccines should be avoided while a patient is on protocol.
- The co-administration of MGCD516 and oral warfarin is possible but should be subject to verification of coagulation (INR) once steady state is reached (after one week's treatment).
- Patients who develop venous thromboembolism (pulmonary embolisms or deep venous thrombosis) may be treated as indicated by LMW heparin and stay on protocol at the discretion of the treating physician.
- The patient will provide a list of concurrent medications related to co-morbidity (e.g. hypertension, diabetes, etc.), including over the counter agents, taken prior to enrollment. The list will be updated during clinic visits while on treatment and will be maintained in the medical record.

Proprietary of MD Anderson Cancer Center

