10.0 EVALUATION DURING TREATMENT

- 10.1 A cycle of treatment is defined as 2 weeks (+/- 3 days), or 4 weeks +/- 3 days if the

Proprietary of MD Anderson Cancer Center

patient is switched to the nivolumab schedule of 480 mg IV every 4 weeks. The following must be performed on Day 1 of each course. If assessment and tests were completed within 7 days of Course 1 Day 1, procedures will not be repeated. Patients are required to come to MD Anderson at the beginning of every course.

- Interim history
- Assessment of Karnofsky performance status, weight, temperature, blood pressure, heart rate.
- Physical examination
- Assessment of all concomitant medications and treatments taken since the last assessment. Concurrent medications related to co-morbidity (e.g. hypertension, diabetes, etc.) will be recorded in the database. The name, dose, date start and stop (as accurately as possible) along with indication of the medication will be collected.
- Assessment of adverse events and tumor-related signs and symptoms
- Assessment of treatment related toxicities
- Laboratory testing:
 - CBC with differential & platelets
 - Chemistry panel including electrolytes (Na, K, Cl, CO₂), alkaline phosphatase, ALT, AST, calcium, total bilirubin, BUN, creatinine
 - Blood for correlative studies
 - Tissue sample

10.2 After 2 weeks (\pm 3 days) of MGCD516 monotherapy: collect blood samples as well as optional fresh biopsy for immune testing and correlative studies to assess treatment response to MGCD516 monotherapy.

10.3 The following labs will additionally be obtained at 6 weeks (42 days +/- 3 days), 12 weeks (84 days +/- 7 days), and every 12 weeks (84 days +/- 7 days) for as long as patients are receiving therapy on protocol :

- Lipids
- Blood glucose
- Serum amylase and lipase
- Serum free T4 and TSH.
- Serum ACTH and Cortisol
- Chemistry panel including electrolytes (Na, K, Cl, CO₂), albumin, alkaline phosphatase, ALT, AST, calcium, LDH, total bilirubin, BUN, creatinine, phosphorus
- Urinalysis: Gross examination including specific gravity, protein, glucose, and blood; microscopic examination including white blood cells / high power field (WBC/HPF), red blood cells / high power field (RBC/HPF) and any additional findings.
 - If urine protein \geq 100 mg/dL then obtain random urine protein/creatinine ratio.

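### Section 6.3 times the warfarin INR check to one week, but the protocol's own PK puts MGCD516 steady state at 11 to 15 days, and no on-treatment INR is scheduled

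*Combined protocol and SAP*

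**What the plan says.** Section 6.3 allows warfarin alongside MGCD516, but co-administration "should be subject to verification of coagulation (INR) once steady state is reached (after one week's treatment".

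Section 3.1.3.1 summarises the first-in-human PK: "The steady state PK is reached in a mean time of 11 to 15 days". It also states: "Mean elimination half-life varies between 40 and 53 hours". On accumulation it says: "Drug accumulation is observed after administration of multiple doses and averages 4.2-fold for" Cmax, and it gives 4.7-fold for AUC over 24 hours. Dosing is once daily (6.2.3).

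Patients on warfarin can enrol. Section 4.2, item 7 reads "Therapeutic anticoagulation with warfarin is allowed if target INR" is no higher than 3 and the dose is stable.

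INR/PTT is a pre-treatment test in Section 9.2. It is absent from the per-cycle list in 10.1 and from the 6-week, 12-week and 12-weekly list in 10.3. Footnote d of the Study Calendar limits it to the pre-study visit. The calendar has no column at one week; after Day +1 the next fixed column is Day +15 (C2D1). For that visit Section 10.1 says "Patients are required to come to MD Anderson at the beginning of every course".

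**The concern.** The protocol gives two different times for the same event. Section 6.3 makes the INR check the condition for using warfarin with MGCD516, so the time printed there is the one an investigator will act on. An INR taken on day 7 satisfies the parenthesis but falls 4 to 8 days before the reported mean time to steady state. No later INR is scheduled that would pick up a further change. The visit that fits the PK, C2D1, has no INR assigned to it.

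What is at stake is safety monitoring in a subgroup: anticoagulation could be judged stable while MGCD516 exposure is still rising.

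**Working it through.** **Inputs.** Half-life t = 40 to 53 h, mean time to steady state 11 to 15 days, and accumulation 4.2-fold (Cmax) and 4.7-fold (AUC), all from 3.1.3.1. Dosing interval 24 h, from 6.2.3. Time in the parenthesis: 7 days, from 6.3. The model is one compartment with first-order elimination. Steady state is taken to mean that of MGCD516.

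**Direct comparison.** 11 − 7 = 4 days and 15 − 7 = 8 days.

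**Can the reported 11 to 15 days be reproduced?** Days to reach a fraction p of plateau = t × log2(1/(1−p)) / 24.

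| Fraction of plateau | t = 40 h | t = 53 h |
|---|---|---|
| 90% | 5.5 days | 7.3 days |
| 95% | 7.2 days | 9.5 days |
| 99% | 11.1 days | 14.7 days |

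The 99% row matches the reported range. One week agrees only with a looser definition, such as 95% at the 40 h end or 90% at the 53 h end. Four half-lives at 40 h gives 4 × 40/24 = 6.7 days.

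**How far short is day 7?** Fraction of plateau after d days = 1 − 2^(−24d/t). Rise still to come = 1/fraction − 1.

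| Days of dosing | t = 40 h | t = 53 h |
|---|---|---|
| 7 | 0.946 (rise 5.8%) | 0.889 (rise 12.5%) |
| 14 (Day 15 visit) | 0.997 (rise 0.3%) | 0.988 (rise 1.3%) |

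**Cross-check from accumulation.** The stated half-life implies R = 1/(1 − 2^(−24/t)), which is 2.94 at 40 h and 3.71 at 53 h. Both are below the stated 4.2 and 4.7. Working backwards, t = 24 × ln 2 / (−ln(1 − 1/R)):

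- R = 4.2 gives 61.2 h, with 0.851 of plateau at day 7 (rise 17.5%) and 0.978 at day 14.
- R = 4.7 gives 69.5 h, with 0.813 at day 7 (rise 23.1%) and 0.965 at day 14.

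These half-lives lie outside the stated range, so one simple model does not fit both inputs. I treat the 81% to 85% figures as secondary. They do show that the accumulation data point towards a later steady state, not an earlier one.

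**The case against.** The strongest reply is that the operative rule is already right. It requires the check at steady state, and the parenthesis can be read as an earliest time, so an INR at C2D1 complies today. That is true, but a day-7 INR complies as well, and it comes before the steady state the protocol itself reports.

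Other points, and what stands of each:

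- **Whose steady state is meant is not stated.** Correct, so I give it as an assumption. MGCD516 is the natural reading, because enrolled warfarin users are already on a stable dose.
- **The gap depends on the definition, and the PK data are early.** This stands. Section 3.1.3.1 does not define steady state. It warns: "Data collection is ongoing, thus all data reported are preliminary". The brochure behind the half-life, accumulation and steady-state figures "includes preliminary PK and PD data collected in the 10 mg to 110 mg cohorts". The same section reports dose-proportional exposure through 200 mg, and nothing in it suggests a shorter time at 120 or 150 mg.
- **A test for a subgroup may sit in the concomitant-therapy section and need not be in the calendar.** Fair. The check is required by 6.3, and Section 14.3 allows tests on clinical indication. The calendar gap matters mainly because the one stated time is wrong and corresponds to no calendar column.
- **Day 15 is only approximate.** Section 10.1 allows ±3 days, so C2D1 can fall on Day 12, after 11 days of dosing. The fraction of plateau is then 0.990 (40 h) or 0.968 (53 h), still clearly better than at day 7. Because 11 to 15 days is a mean, some patients will take longer.
- **The 42 patients in Section 3.4 enrolled by February 2020.** Their first weeks of dosing are past, which limits the practical effect.

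**Conclusion.** The concern holds as a minor error: the time in the parenthesis of Section 6.3 is wrong as written. It is 4 to 8 days earlier than the steady-state time in Section 3.1.3.1, and no visit carries a later INR. On the stated half-life, a day-7 check sees about 89% to 95% of plateau exposure. On the accumulation figures it could be as low as 81% to 85%, with the caveat above.

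The conclusion that the two times conflict rests only on reading steady state as that of MGCD516. The percentages also need one-compartment kinetics and the preliminary PK values. None of them measures an error in INR, and the harm cannot be sized from the documents. Dose-finding, endpoints and analysis do not change.

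**What to change.** In Section 6.3, replace the one-week time and keep an early check, for example: *INR at about one week, and again once MGCD516 steady state is reached (about 15 days; C2D1 visit)*. Add a footnote to the INR/PTT row of the Study Calendar requiring INR at C2D1 for patients on warfarin.

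The cost is one phrase and one footnote. Patients already attend on Day 15 and Section 6.3 already calls for an INR after about a week, so the added burden is one INR at an existing visit for warfarin users only. The change removes no existing check.

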6.4 Dose Modifications and Interruptions

There will be no intra-subject dose reduction or escalation of nivolumab during the study. Patients will continue to receive MGCD516 daily along with nivolumab 240 mg IV every 2 weeks until disease progression or unacceptable treatment-related DLT. Patients who have received at least 6 infusions of nivolumab 240 mg IV every 2 weeks with no DLT related to nivolumab, will be allowed to transition to the equivalent nivolumab schedule of 480 mg IV every 4 weeks. If one agent (MGCD516 or nivolumab) is interrupted or discontinued, administration of the other agent may continue at the discretion of the Investigator and patient.

There are four possible dose levels for MGCD516 in this study: 60, 80, 120, and 150 mg per day. Depending on safety observations, the MGCD516 dose during subsequent cycles of treatment may be reduced to the next lower dose level at the discretion of the Investigator and patient. Specifically, for grade ≥ 3 hematologic and non-hematologic DLTs or Grade ≥ 2 drug-related uveitis that does not respond to topical therapy OR requires systemic treatment (as described in section 5.3) attributed to MGCD516 then treatment should be held until resolution to \leq Grade 1 or baseline, and then MGCD516 can be restarted at the next lower dose level. If toxicity recurs (second time or third time) at Grade ≥ 3 (or Grade ≥ 2 drug-related uveitis that does not respond to topical therapy OR requires systemic treatment), then hold MGCD516 until resolution to \leq Grade 1 or baseline and restart at next lower dose level. If the patient develops a DLT related to MGCD516 at the 60 mg dose level then MGCD516 should be discontinued. Dose reductions of MGCD516 will also be allowed on a case-by-case basis at the discretion of the Investigator and patient in patients with toxicity related to MGCD516 that does not meet the DLT criteria outlined in section 5.3. Once the dose has been reduced, re-escalation is generally not recommended but may be considered on a case-by-case basis. If the administration of MGCD516 is interrupted for reasons other than toxicity, then treatment with MGCD516 may be resumed at the same dose. Only the data from the originally planned MGCD516 dose will be used for the dose-finding late-onset EffTox (Lo-EffTox) calculations, described in section 14.

Dosing interruptions > 4 weeks that occur for non-drug-related reasons may be allowed if approved by the Principal Investigator. Prior to re-initiating treatment in a subject with a dosing interruption lasting > 4

Proprietary of MD Anderson Cancer Center

weeks, the UTMDACC IND Office must be notified. Tumor assessments should continue as per protocol even if dosing is interrupted.

As described above, after the patient has received at least 2 infusions of nivolumab and 6 weeks (42 days) of oral MGCD516 then further combination treatment can be held for up to 4 weeks (28 days) to allow for recovery from surgery, radiation therapy, or other interventions for palliation purposes or management of intercurrent illness which, in the judgement of the treating physician, is not related to disease progression.

Immune-related Adverse Events (irAEs) are defined in the nivolumab label as those occurring during nivolumab therapy, often necessitate immunosuppression and have no other alternate etiology. The nivolumab package insert (http://packageinserts.bms.com/pi/pi_opdivo.pdf) provides detailed evaluation and management guidelines for the following types of ir-AEs: pneumonitis, colitis, hepatitis, endocrinopathies, nephritis/renal dysfunction, rash, and encephalitis. As a general principle, nivolumab should be withheld or permanently discontinued in patients with moderate or severe irAEs. Depending on the nature of the irAE, it should be managed with corticosteroids and/or hormone-replacement therapy. The corticosteroids should be tapered down upon improvement of the irAE to Grade ≤ 1 . Depending on the severity of the irAE, restarting of nivolumab may be considered. Prior to re-initiating treatment in a subject with a dosing interruption lasting > 28 days, the UT MDACC IND Office must be consulted. Tumor assessments should continue as per protocol even if dosing is interrupted.

Patients experiencing any Grade 4 non-hematological toxicity should be taken off study. MGCD516 can be held in patients experiencing, despite optimal supportive care, persistent non-overlapping toxicities attributed to MGCD516, such as hypertension, palmar-plantar erythrodysesthesia, peripheral neuropathy, or stomatitis. The Principal Investigator must be consulted prior to re-initiating treatment in a subject with a dosing interruption lasting > 4 weeks.

With regards to the management of potential overlapping toxicities of the two drugs:

- Patients experiencing Grade 3 fatigue for > 5 days despite optimal supportive care should be taken off study with discontinuation of the combination therapy.
- In patients experiencing Grade 3 rash or Grade 2/3 diarrhea, both oral MGCD516 and nivolumab should be held until improvement to Grade ≤ 1 . Topical and/or systemic steroids can be given as needed. If no improvement to \leq Grade 1 after combination treatment has been held for > 3 weeks then the patient should be taken off study. Dosing interruptions for prolonged steroid tapers > 6 weeks to manage drug-related adverse events are allowed. The Principal Investigator must be consulted prior to re-initiating treatment in a patient with a dosing interruption lasting > 4 weeks.
- Patients experiencing Grade 3/4 elevation in serum amylase and/or lipase levels associated with clinical or radiological evidence of pancreatitis, with no other alternate etiology, should be taken off study with discontinuation of the combination therapy.

Discontinuation criteria for nivolumab and MGCD516 are described in sections 8.1 and 8.2, respectively.

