2.0 OBJECTIVES

Primary objective:

- To determine the toxicities (defined as a grade 3 or 4 NCI CTCAE non-hematologic or hematologic adverse event, within 12 weeks from treatment initiation), and efficacy (defined as achieving complete remission, partial remission, or stable disease within 6 weeks) of MGCD516 when administered PO daily in combination with standard dose nivolumab 240 mg IV every 2 weeks.

Secondary objectives:

- To estimate the overall survival (OS), progression-free survival (PFS) times, objective response rates (ORR), and quality of life (QOL) of patients with advanced clear cell RCC treated with the combination of MGCD516 and nivolumab
- Evaluate potential biomarkers for patient stratification and treatment response, including genetic analysis, serum cytokines and chemokines, as well as tumor antigen-specific immune responses, such as antibody and T cell responses, as surrogates for anti-tumor activity

Extended Access objective (long term extension phase):

- Provide continued access to MGCD516 (sitravatinib) in combination with nivolumab, with continued collection of serious adverse events, for patients enrolled on trial and continue to benefit from this combination regimen.

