5.3 Study Design and Duration

This is a phase I-II dose-finding trial to determine the optimal dose of the targeted oral agent MGCD516 when combined with immunotherapy via intravenous Nivolumab at fixed dose 240 mg IV every 2 weeks, in patients with metastatic renal cell carcinoma with a clear cell component who have progressed following treatment with anti-VEGF agents. The goal of the study is to determine an optimal oral MGCD516 dose level among the four levels 60, 80, 120

Proprietary of MD Anderson Cancer Center

and 150 mg/day given orally daily until toxicity or progressive disease. Dose-finding will be done using the sequentially adaptive phase I-II late-onset EffTox (Lo-EffTox) trade-off-based design of Jin et al.⁶⁰⁻⁶² To determine the optimum dosage, efficacy is defined as achieving complete response (CR), partial response (PR), or stable disease (SD) within 6 weeks, and the occurrence of any of the following toxicities within 12 weeks from the start of therapy will be considered a dose-limiting **toxicity** (DLT), if judged by the Investigator to be clinically relevant and related (possibly or probably) to administration of either or both study drug(s):

- Hematologic DLTs:
 - Grade ≥ 3 febrile neutropenia ($ANC < 1.0 \times 10^9/L$ with either a single temperature $\geq 38.3^{\circ}C$ or a sustained temperature of $\geq 38^{\circ}C$ for more than 1 hour)
 - Grade 3 thrombocytopenia (platelets $< 50.0 \times 10^9/L \geq 25.0 \times 10^9/L$) if associated with:
 - A bleeding event that requires an elective platelet transfusion, OR
 - A life-threatening bleeding event which results in urgent intervention and admission to an Intensive Care Unit
 - Grade 4 thrombocytopenia (platelets $< 25.0 \times 10^9/L$)
- Non- Hematologic DLTs:
 - Any Grade 4 non-hematological toxicity
 - Grade ≥ 2 drug-related uveitis that does not respond to topical therapy OR requires systemic treatment
 - Grade 3 overlapping toxicities of nivolumab and MGCD516, including diarrhea, rash, fatigue, or elevation of serum amylase/lipase, lasting > 3 days despite optimal supportive care with the exception of:
 - Grade 3 fatigue lasting ≤ 5 days
 - Grade 3 rash that resolves to \leq Grade 1 within 3 weeks
 - Grade 3/4 elevation in serum amylase and/or lipase that are not associated with clinical or radiological evidence of pancreatitis
 - Any other Grade 3 non-hematologic toxicity lasting > 3 days despite optimal supportive care with the exception of:

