8.1 Discontinuation Criteria of Nivolumab

Nivolumab administration should be discontinued for the following:

- Any Grade \geq 2 drug-related uveitis, eye pain, or blurred vision that does not respond to topical therapy and does not improve to Grade 1 severity within the re-treatment period OR requires systemic treatment
- Any Grade 3 non-skin, drug-related adverse event lasting > 7 days, with the following exceptions for laboratory abnormalities, drug-related bronchospasm, hypersensitivity reactions, and infusion reactions:
 - Grade 3 drug-related laboratory abnormalities do not require treatment discontinuation except:
 - Grade 3 drug-related thrombocytopenia > 7 days or associated with bleeding requires discontinuation.
 - Any drug-related liver function test (LFT) abnormality that meets the following criteria require discontinuation:
 - Aspartate aminotransferase (AST) or alanine aminotransferase (ALT) $> 5-10x$ upper limit of normal (ULN) for > 2 weeks
 - AST or ALT $> 10x$ ULN
 - Total bilirubin $> 5x$ ULN
 - Concurrent AST or ALT $> 3x$ ULN and total bilirubin $> 2x$ ULN
 - Grade 3 drug-related bronchospasm, hypersensitivity reaction, or infusion reaction of any duration requires discontinuation

Proprietary of MD Anderson Cancer Center

- Any Grade 4 drug-related adverse event or laboratory abnormality, except for the following events which do not require discontinuation:
 - Grade 4 neutropenia \leq 7 days
 - Grade 4 lymphopenia or leukopenia
 - Isolated Grade 4 electrolyte imbalances/abnormalities that are not associated with clinical sequelae and are corrected with supplementation/appropriate management within 72 hours of their onset.
 - Grade 4 amylase or lipase abnormalities that are not associated with symptoms or clinical manifestations of pancreatitis. It is recommended to consult with the PI for Grade 4 amylase or lipase abnormalities.
- Any dosing interruption lasting $>$ 4 weeks with the following exceptions:
 - Dosing interruptions to allow for prolonged steroid tapers to manage drug-related adverse events are allowed. Prior to re-initiating treatment in a subject with a dosing interruption lasting $>$ 4 weeks, the Principal Investigator must be consulted. Tumor assessments should continue as per protocol even if dosing is interrupted.

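### Sections 5.3, 6.4 and 8.1 give conflicting stopping rules for Grade 4 non-hematologic toxicity and prolonged Grade 3 fatigue, and Grade 4 amylase/lipase elevation both is and is not a DLT

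*Combined protocol and SAP*

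**What the plan says.** **DLT definition.** Section 5.3 counts "Any Grade 4 non-hematological toxicity" as a DLT. Under the separate bullet on Grade 3 overlapping toxicities it exempts "Grade 3/4 elevation in serum amylase and/or lipase that are not associated with clinical or radiological evidence of pancreatitis", and also "Grade 3 fatigue lasting ≤ 5 days". All of these fall under a lead-in that requires the investigator to judge the event clinically relevant and related to a study drug. Section 2.0 describes the primary toxicity differently: "defined as a grade 3 or 4 NCI CTCAE non-hematologic or hematologic adverse event, within 12 weeks from treatment initiation", with no relatedness, duration or exception terms.

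**Stopping rules in Section 6.4.** For Grade 3 or higher DLTs attributed to MGCD516, the drug is held until recovery, "and then MGCD516 can be restarted at the next lower dose level". A later paragraph says "Patients experiencing any Grade 4 non-hematological toxicity should be taken off study". The list of overlapping toxicities then says "Patients experiencing Grade 3 fatigue for > 5 days despite optimal supportive care should be taken off study", with both drugs discontinued. The same list takes patients with Grade 3/4 amylase/lipase elevation off study when there is evidence of pancreatitis.

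**Stopping rules for nivolumab.** Section 8.1 stops nivolumab for Grade 4 drug-related events, but lists exceptions. They include "Grade 4 amylase or lipase abnormalities that are not associated with symptoms or clinical manifestations of pancreatitis" and isolated electrolyte abnormalities corrected within 72 hours. It stops nivolumab for Grade 3 non-skin drug-related events that last more than 7 days. Sections 6.4 and 8.0 also allow one agent to continue when the other is stopped.

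**The concern.** A protocol should give one instruction per event, and here the same event falls under two or three rules with different outcomes. Two things are at stake.

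First, conduct. Whether a patient leaves the study or resumes MGCD516 at a lower level changes exposure and can change later follow-up for PFS, OS and quality of life.

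Second, the dose-finding outcome. DLT within 12 weeks is the toxicity variable in the Lo-EffTox model (Sections 5.3 and 14.1). If one kind of event can be classified either way, the toxicity data depend on which bullet the assessor applied.

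**Working it through.** The plan gives no figure for this point, so the check is mainly a comparison of the rules.

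**1. Grade 4 non-hematologic toxicity attributed to MGCD516**

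| Place | Instruction |
|---|---|
| 5.3 | DLT |
| 6.4, DLT management | Hold, may restart MGCD516 one level lower (Grade 3 or higher includes Grade 4) |
| 6.4, later paragraph | Off study, no attribution condition, no laboratory exception |
| 6.4, overlapping toxicities | Amylase/lipase Grade 3/4: off study if there is pancreatitis |
| 8.1 | Nivolumab need not stop for Grade 4 amylase/lipase without pancreatitis or for isolated, corrected electrolyte abnormalities |

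Read literally, the off-study rule removes the restart option. It also makes the pancreatitis condition idle for Grade 4, and it leaves the 8.1 exceptions for Grade 4 amylase/lipase and electrolytes without effect.

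**2. Grade 3 fatigue lasting more than 5 days**

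The DLT threshold is consistent: 5.3 exempts fatigue up to 5 days, and 6.4 acts beyond 5 days. The stopping instructions differ. As a DLT attributed to MGCD516 it allows hold and restart (6.4). As an overlapping toxicity it means off study with both drugs stopped (6.4). As a Grade 3 non-skin event it stops nivolumab only after 7 days (8.1).

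**3. What counts as a DLT**

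Within 5.3, a Grade 4 amylase/lipase elevation without pancreatitis meets the unqualified Grade 4 bullet and also the exception under another bullet. The relatedness judgement does not settle this, because it governs both bullets. Section 2.0 would count the event as toxicity in any case.

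**4. How much one classification could matter (illustration)**

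Inputs:
- Section 3.4: 4/15 DLTs at 80 mg, 10/24 at 120 mg, 3/3 at 150 mg.
- Section 14.1: toxicity limit .40, cut-off .10, prior mean toxicity .30 at 120 mg, overall prior effective sample size 1.

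Total DLTs are 4 + 10 + 3 = 17, and 17/42 = 40.5%. The documents do not break these down by type, so the number open to reclassification is unknown. A shift of one patient in either direction is assumed.

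Single-dose approximation: with x DLTs in n = 24 and prior Beta(.30, .70),

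P(pT < .40) = F(.40; .30 + x, .70 + 24 − x), where F is the Beta distribution function.

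| x | x/24 | P(pT < .40) |
|---|---|---|
| 9 | 37.5% | 0.63 |
| 10 (reported) | 41.7% | 0.46 |
| 11 | 45.8% | 0.31 |
| 12 | 50.0% | 0.18 |
| 13 | 54.2% | 0.09 |

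A flat Beta(1, 1) prior gives 0.58 for x = 9, 0.41 for x = 10 and 0.08 for x = 13. Under either prior the value falls below .10 only at 13/24, three more DLTs than reported. This is not the Lo-EffTox model, which borrows across doses and models efficacy jointly.

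**The case against.** The best defence is that specific rules override general ones. The restart wording is permissive and limited to events attributed to MGCD516, so taking a patient off study does not breach it. The fatigue rule sits in a list specific to overlapping toxicities. The 7-day nivolumab rule can be read as a backstop that a patient stopped after 5 days never reaches. The figure 4 in the amylase/lipase exception has no purpose unless it carves out of the Grade 4 bullet. Treatment decisions rest with the principal investigator or designee (6.1.3), who is also final arbiter of toxicity (15.0).

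This is a reasonable way to read the text, but the text does not say it. The restart rule itself names Grade 3 or higher non-hematologic DLTs, the off-study rule has no exception for the laboratory events in 8.1, and 6.4 refers to 8.1 and 8.2 without ranking them. Central control settles who decides, not which rule applies.

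Three stronger readings are tempting but not supported:
- **That the fatigue DLT definition is also inconsistent.** It is not; only the stopping rules differ.
- **That patients taken off study give no further data.** Section 12.0 says this of study withdrawal. Section 8.0 requires at least weekly follow-up of suspected drug-related events after treatment stops, 10.7 asks for every effort at imaging when toxicity stops treatment before restaging, and 10.8 provides survival follow-up. Moreover, once a DLT has occurred the Lo-EffTox toxicity outcome is already set, so the stopping conflict does not alter it.
- **That crossing 40% at 120 mg changes the dose decision.** The acceptability rule uses a posterior probability with a .10 cut-off, not the raw rate.

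**Conclusion.** The concern holds: the plan is wrong as written. The stopping instructions conflict for Grade 4 non-hematologic toxicity and for Grade 3 fatigue beyond 5 days. The DLT definition conflicts for Grade 4 amylase/lipase elevation without pancreatitis, and Section 2.0 states a broader toxicity than 5.3. No precedence is given.

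The numerical effect is unknown. A reader might infer that the reported DLT counts are wrong or that the choice of 120 mg is unsafe statistically; the documents show neither. No affected patient is identified. One reclassified patient at 120 mg would not by itself change acceptability, on the assumption that the single-dose approximation is a fair guide. The effect on the desirability scores in Section 3.4 (0.787 at 80 mg, 0.755 at 120 mg) cannot be derived from the documents.

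**What to change.** - Reconcile Sections 2.0, 5.3, 6.4, 8.0 and 8.1 into one table of event and grade, with one action for MGCD516 and one for nivolumab, and state which section prevails if texts differ.
- State once whether Grade 4 amylase/lipase elevation without pancreatitis is a DLT, and align the toxicity wording of Section 2.0 with 5.3.
- Check the DLT listing behind the counts in Section 3.4 against that definition. If a count changes, rerun the dose-finding posteriors and report both versions.

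Which clinical rule stands is for the sponsor's clinical team. The cost is amendment wording and a review of the DLT listing, with 17 reported DLTs among 42 patients. No new data collection is needed.
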